## 3.2 Participants

Subjects will be recruited among patients with TBI admitted to the emergency department, trauma, or neurosurgical services at 5 participating TRACK-TBI Clinical Sites. Each site has a system for identification and early notification of potential patients who qualify for the study. The early notification system will result in timely arrival of the study coordinator or other trained study personnel, who will evaluate a participant's eligibility. Individuals notifying study personnel of potential patients may include ambulance coordinating system personnel, neurosurgery residents, emergency room physicians, or other hospital personnel who are likely to see brain injured patients shortly after their arrival.

Once notified, study personnel will review the potential patient's information and screen the patient according to the study inclusion and exclusion criteria (Table 3). Upon determining that the patient is potentially eligible for the study, consent will be obtained from the patient or the legally authorized representative (LAR) according to local IRB guidelines. If the patient is determined to have capacity to provide his or her own consent, the patient will be asked to provide informed consent. For participants whose LAR originally gave consent, an informed consent will be obtained from the participant once they have the capacity to do so. The target enrollment for this study is 50 participants.

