#### 3.4 Milestone Plan

Our target follow-up rate for the 3-month duration of the study is 80%. The Clinical Core will monitor this rate at the overall study level as well as the individual site level. Women and minorities will be included.

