## **5.3 Participation Requirements**

An important part of the screening and enrollment process is an interview with the subject, where the research personnel explains the project in detail, presents the consent forms, and responds to all patient questions and concerns. Key points that will be explained during this interview process are:

• Participation in the project is immediate and for all components (clinical, biospecimens, MRI, outcomes), unless contraindicated for MRI.

- Potential subjects will be given time to read the Consent Form(s) and to consult with family members who may be present or by phone. If the subject agrees to participate, then they will sign the appropriate forms. A copy of the form(s) will be given to the subject.
- Upon enrollment, data collection will begin in the hospital. Participation in follow-up activities must be completed within given follow-up assessment windows as specified below (Table 4), but will be scheduled to accommodate the patient:

**Table 4**. Schedule for Follow-Up (FU) Assessment Windows

In-person 2 Week Follow-up Assessment Windows			
2 Wook FU	MRI: 14 days post-injury ± 4 days		
2 Week FU	Outcomes + blood collection: ± 3 days of 2-week MRI		

In-person 6 Week Follow-up Assessment Window		
6 Week FU	Outcomes + blood collection: 42 days post-injury ± 4 days	

In-person 3 Month Assessment Window			
3 Month FU	MRI: 90 days post-injury ± 14 days		
3 WIOIILII FO	Outcomes + blood collection: ± 3 days of 3 month MRI		

- All efforts should be made to schedule patient return within the specified window for each time point.
  Patients who are reached and scheduled but fall outside the window for any outcomes testing time point should still have their outcomes assessment completed during the next scheduled follow-up time point.
  The number of days from date of injury, and the number of days outside of the exact 2-week, 6-week, and 3-month, window will be documented in the QuesGen database.
- Compensation is provided for participation in each study activity. See section 5.4 Subject Compensation for further information.

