- (iv) The waiver or alteration will not adversely affect the rights and welfare of the subjects. The primary risks of this observational study is loss of privacy and standard risks associated with a blood draw. We have taken steps to ensure the privacy of subjects. In most cases, blood draws will be collected through already placed arterial lines and/or at the same time of clinically indicated blood draws, and thus, there will be minimal to no additional risks associated with these blood draws. Furthermore, in the event that patient or LAR consent cannot be obtained by the time of the 2 week study visit, all data collected on the patient, including blood collected and processed, will be discarded (will not be analyzed, banked, or shared with collaborators); (v) Whenever appropriate, the subjects or LAR will be provided with additional pertinent information after participation. We will make every effort to obtain patient or LAR consent as soon as possible after enrollment under waiver. A copy of the consent form as well as a study summary document that summarizes the pertinent details about the study will be left at the bedside of a patient enrolled under Waiver of Consent, and study staff will stay in touch with hospital staff to monitor the patient's status while inpatient. If a patient is discharged while still under waiver, then the patient will be discharged with a copy of the consent form, a study summary document that summarizes the pertinent details about the study, and contact information for study staff. Study staff will approach in-person (if the patient remains inpatient/the LAR presents to the bedside) or by phone (if the patient is discharged/a LAR is identified who is off-site) to complete the informed consent process as soon as the patient may be able to consent for her/himself and/or a LAR presents her/himself. If self or LAR consent is not obtained by the time of the 2 week study visit, then all data and blood collected under waiver will be destroyed/discarded.

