#### 7.2 Biospecimens Procedures.

We will obtain 12.0 ml of blood at each of the following time points: within 6 hours of injury, and again at 12h, 24h, 2d, 3d, 5day, 2w, 6w and 3m post-injury (See **Table 6**: Biospecimen Sample Collection Schedule below). Every blood draw will be optional. The TRACK-TBI Precision Medicine procedures around collection, processing, storage, and shipping of biospecimens collected during the in-person assessment will align with the TRACK-TBI U01 procedures (see Appendix 2: TRACK-Precision Medicine\_Biospecimen Protocol\_MOP\_v1.5\_APR062021, also saved on the Study Shared BOX folder at: TRACK-TBI Precision Medicine Study Documents\Biospecimens core\Biospecimens MOP).

- Collection at each time point will consist of one 6.0 ml lavender EDTA tube (plasma and buffy coat) and one 6.0 ml red top tube (serum).
- Whole blood will be processed for serum, plasma, and buffy coat. Serum and plasma will be stored in 500 µl aliquots for future analyses.

**Table 6**. Biospecimen Sample Collection Schedule

<6	12	24	Day	Day	Day	Day	Day	Day
hr	hr	hr	2	3	5	14	42	90
12	12	12	12	12	12	12	12	12
mL	mL	mL	mL	mL	mL	mL	mL	mL
	hr 12	hr hr 12 12	hr         hr         hr           12         12         12	hr         hr         hr         2           12         12         12         12	hr         hr         hr         2         3           12         12         12         12         12	hr         hr         hr         2         3         5           12         12         12         12         12         12	hr         hr         hr         2         3         5         14           12         12         12         12         12         12         12	hr         hr         hr         2         3         5         14         42           12         12         12         12         12         12         12         12

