#### MRI Statistical Considerations

We will calculate Pearson's correlation of each of the baseline early (<6 hours to 1 week) blood-based biomarkers, with the corresponding MRI markers that look promising based on Phase 1 results. There will be no adjustment for multiple comparisons as these comparisons are exploratory given the paucity of information about the time-course of these markers in people with TBI. ROC analysis will be performed to determine the discriminative ability of the blood-based and imaging biomarkers in predicting outcomes. AUC will be calculated and reported along with 95% confidence intervals. Prediction increment will be measured by change in AUCs calculated based on logistic regression models.

Adequacy of sample size: With 50 participants, using correlation power analysis, we have at least 80% power to detect a correlation of .38 or greater.

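### The 80% power claim for a correlation of .38 treats all 50 enrolled participants as complete blood-MRI pairs; at the protocol's own 80% follow-up target, power is about 69%

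*Protocol*

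**What the plan says.** Section 7.3 (MRI Statistical Considerations) plans Pearson correlations of early blood markers, from under 6 hours to 1 week after injury, with the corresponding MRI markers. It justifies the sample size with "With 50 participants, using correlation power analysis, we have at least 80% power to detect a correlation of .38 or greater". It gives no alpha, sidedness or formula, and no allowance for missing blood or MRI. It describes the comparisons as exploratory and says "There will be no adjustment for multiple comparisons".

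The 50 is the enrolment figure. Section 3.2 says "The target enrollment for this study is 50 participants", with no inflation for loss.

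Other sections bear on how many of the 50 will have both values:

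- Section 3.4 says "Our target follow-up rate for the 3-month duration of the study is 80" percent. Section 15.1 treats 80% as something each site must reach, and Section 17.2 applies it across all time points.
- Table 4 (Section 5.3) places MRIs at 14 ± 4 days and 90 ± 14 days as follow-up visits. MRI Procedures (Section 7.3) confirms a 3-month follow-up scan for all patients.
- Section 7.2 says "Every blood draw will be optional".
- Section 13 lets outcomes be collected by phone when an in-person visit cannot be arranged. Such a visit yields neither blood nor MRI.

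**The concern.** A correlation is computed on pairs, so its power depends on the number of participants with both a usable early blood value and a usable MRI. The power statement takes that number to be everyone enrolled. The same protocol sets an 80% follow-up target and puts the 2-week and 3-month scans inside follow-up, so its planning figures do not agree.

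At stake is how the results can be read. With about 40 pairs, the chance of missing a true correlation of .38 is about 31%, against the 20% at most that the sentence implies. Someone relying on the sentence would credit the study with more ability to detect moderate correlations than it has at its own follow-up target.

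**Working it through.** **Inputs**

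- Correlation .38 and power of at least 80%: Section 7.3, MRI Statistical Considerations.
- n = 50: the same sentence, equal to the enrolment target in Section 3.2.
- Follow-up of 80%: Sections 3.4, 15.1 and 17.2. This gives 0.80 × 50 = 40 pairs.
- An intermediate case of 90% (assumed): 0.90 × 50 = 45 pairs.
- Alpha of 5%, two-sided (assumed, because the protocol does not state it).

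**Formula**

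With the Fisher z approximation, power ≈ Φ(atanh(r)·√(n − 3) − 1.960), and the correlation detectable at 80% power is tanh((1.960 + 0.842)/√(n − 3)). Here atanh(.38) = 0.400.

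**Reproducing the stated figure, n = 50**

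- 0.400 × √47 = 2.743.
- 2.743 − 1.960 = 0.783, and Φ(0.783) = 0.783.
- Detectable r = tanh(2.802/6.856) = .387.

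**Reduced numbers of pairs**

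- n = 45: 0.400 × √42 − 1.960 = 0.633, power 0.737.
- n = 40: 0.400 × √37 − 1.960 = 0.474, power 0.682. Detectable r = tanh(2.802/6.083) = .431.

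**Sensitivity to the formula (two-sided 5%, r = .38)**

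| Method | 50 pairs | 45 pairs | 40 pairs |
|---|---|---|---|
| Fisher z | 0.7831 | 0.7365 | 0.6821 |
| Fisher z with bias term and t-based critical r | 0.7901 | 0.7446 | 0.6914 |
| Exact bivariate normal | 0.7914 | 0.7462 | 0.6930 |
| Noncentral t, fixed X | 0.8123 | 0.7685 | 0.7164 |
| Detectable r at 80% power (exact; Fisher z) | .3837; .3873 | .4031; .4072 | .4257; .4306 |

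The 50-pair column straddles 80%, so the printed claim reproduces within rounding and choice of formula, but only with no missing pairs.

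**Sensitivity to sidedness**

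A one-sided 5% test gives 86-87% at n = 50 and 78-80% at n = 40. The first range is well above 80%, so one-sided testing fits a threshold of .38 less closely than two-sided testing does.

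**The case against.** The strongest reply has three parts.

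First, 80% is a target and a required minimum, not a prediction. Early blood may be paired with the 2-week MRI, and loss by then may be smaller than at 3 months. This stands, and it is why 40 pairs is presented as what follows if the target is just met. But 45 pairs also fall below 80% power under all four formulas, and 40 is not a floor either, given optional draws and phone visits.

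Second, the timing of the acute MRI is itself inconsistent. MRI Procedures limits the 48-hour scan to 20% of patients. Table 2, the Neuroimaging paragraph of Section 12.1 and the deviation list in Section 17.2 mention it without that limit. If everyone were scanned within 48 hours, pairs formed from that scan would not depend on follow-up. This also stands. For the same reason a reader should not infer a 10-pair analysis with very low power: that takes one side of an unresolved conflict, and the power sentence makes no claim about that subset.

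Third, the analysis is exploratory and no decision rule hangs on a non-significant correlation. This limits the consequence but does not make the sentence right.

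Three further inferences are tempting, and the protocol does not support them:

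- *That the sentence is wrong even with 50 pairs.* The range of 78-81% is rounding and choice of formula.
- *That destroyed waiver data reduce the 50.* Section 6.8 says that, if consent is not obtained by the 2-week visit, "then all data and blood collected under waiver will be destroyed/discarded". It also says such patients are removed from the study, and nothing says they count toward the 50.
- *That participants with an MRI contraindication are planned for.* Section 5.3 says "Participation in the project is immediate and for all components (clinical, biospecimens, MRI, outcomes), unless contraindicated for MRI", but inclusion criterion 5 requires ability to undergo MRI, and Section 12.1 says screening will keep such people out. This is a separate inconsistency, not a known loss of pairs.

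**Conclusion.** The concern holds for the number of pairs. The claim of "at least 80% power to detect a correlation of .38 or greater" rests on 50 complete pairs from 50 enrolled, a yield that the protocol's own follow-up target does not assume. At two-sided 5%, power for .38 is about 69% (68-72% by formula) with 40 pairs and about 74-77% with 45. The correlation detectable at 80% power moves from about .38 to about .43 when pairs fall from 50 to 40.

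This rests on three assumptions: alpha and sidedness as above, the MRI being a 2-week or 3-month scan, and follow-up just meeting 80%. The arithmetic of the stated figure is not in dispute; the input n is. Because the comparisons are exploratory and the shift in detectable correlation is modest, this is a correction to make at the next protocol revision. It does not threaten the study.

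**What to change.** Restate the sample-size sentence on expected complete pairs and give alpha and sidedness. For example:

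> With 50 complete blood-MRI pairs, power is about 80% (two-sided 5%) for r = .38. At the 80% follow-up target, about 40 pairs give 80% power for r of .43 or more, and about 69% for r = .38.

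This costs one sentence and a slightly less favourable detectable correlation; no extra enrolment is needed. If the sponsor preferred to keep 50 pairs at 80% follow-up, that would take 50/0.80 = 62.5, so 63 enrolled, but the wording change is enough.

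Separately, the MRI-contraindication wording in Section 5.3 and inclusion criterion 5 in Table 3 should be reconciled.

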#### 7.4 Outcomes

All clinical outcome assessment (COA) measures will be obtained from the patient, or if cognitively unable, the surrogate (i.e., caregiver). The enrollment outcome assessment battery will be obtained at consent or by

phone within 24 hours of injury. It will be administered only to participants who score ≥75 on the Galveston Orientation and Amnesia Test (GOAT). At subsequent follow-up visits, the participants will undergo in-person outcomes testing according to the Flexible Outcome Assessment Battery Decision Workflow (see Figure 1) at 2 weeks, 6 weeks, and 3 months from the time of injury. All measures that can be collected by phone will be collected by phone (see Section 8 TRACK-TBI PRECISION MEDICINE ASSESSMENT BATTERY AND ORDER OF ADMINISTRATION tables below), if study staff cannot administer in person.

## Flexible Clinical Outcome Assessment (COA) Battery Framework

The Flexible Outcome Assessment Battery is designed to assess multiple outcome domains across all phases of recovery in patients at all levels of TBI severity. The battery comprises the original Core CDE measures (TBI-CDE Version 1.0) administered in the TRACK-TBI Pilot study, and additional Basic and Supplemental CDEs (TBI-CDE Version 2.0) that further assess psychological health and cognition. The combined TBI-CDE versions constitute the Comprehensive Assessment Battery (detailed in section 8.2 below). Patients who are too impaired to tolerate the Comprehensive Assessment Battery will undergo assessment on the Abbreviated Assessment Battery (detailed in section 8.3 below), which consists of standardized measures of basic neurobehavioral (e.g., Coma Recovery Scale-Revised [CRSR]) and cognitive (e.g., Confusion Assessment Protocol [CAP]) function. See Figure 1 for the Flexible Outcomes Assessment Battery Framework Decision Workflow.

[figure not shown]
Minimizing in-person outcome assessment procedures and conducting remote outcome assessment To accommodate any current and future local restrictions on research study activities during COVID-19, and other similar circumstances, sites should comply with local practices/guidance and reach out to UCSF if they require further guidance on completion of TRACK-TBI-related study activities. The utility and necessity of these

procedures will be evaluated over time to see if they need to be modified due to COVID-19, or kept in place after COVID-19 restrictions are lifted.

- Self-report/Interview measures: If the PI and study team deem that it is safer to minimize study staff and subject face-to-face contact for study visits that would otherwise be in-person, all self-report and interview outcome measures can and should be completed remotely (e.g., telephone, secure Zoom, or other supported and secure platform) with application of the appropriate test completion code of "1.3 valid administration collected by phone" (even when using Zoom or other, similar platform) with a note added into QuesGen that the visit was conducted by phone due to COVID (or other similar circumstance).
- Performance Measures: If it is possible to conduct a shortened in-person visit to administer the cognitive measures that must be collected in-person, sites should do so following all TRACK-TBI procedures and implementing all local safety practices. If it is deemed unsafe to have a shortened in-person visit to collect these cognitive measures, a test completion code of "3.6 Test not attempted due to logistical reasons" should be entered on the electronic and paper CRFs (if paper CRFs are able to be used) with a note added into QuesGen that the visit was conducted by phone due to COVID (or other similar circumstance).
- In-person procedures that cannot be completed remotely: MRI and blood collection procedures can only be conducted in-person and should only be attempted once TRACK-TBI leadership has given approval, and any local restrictions on in-person research study activities has been lifted.
- ❖ Paper case report form completion during remote study activities: The standard for TRACK-TBI studies is to directly enter data onto paper case report forms and then enter the data into the QuesGen electronic database. If remote collection of data is necessary and access to a printer is limited, direct data entry into QuesGen is acceptable.

Figure 1: Flexible Outcomes Assessment Battery Framework: Decision Workflow

# TRACK TBI Precision Medicine Flexible Outcome Battery Flow Chart

# 8 TRACK-TBI PRECISION MEDICINE FLEXIBLE OUTCOME ASSESSMENT BATTERY AND ORDER OF ADMINISTRATION

## 8.1 Enrollment Battery (at consent or by phone within 24 hours of injury): ~11 minutes

- 1. Rivermead Post Concussion Symptoms Questionnaire (RPQ): 3 mins
- 2. Brief Symptom Inventory 18 (BSI-18): 3 min
- 3. Standard Assessment of Concussion\* (SAC): 5 min

The enrollment outcome assessment battery will be administered only to participants who score ≥75 on the Galveston Orientation and Amnesia Test (GOAT).

## 8.2 Comprehensive Assessment Battery (CAB) (2 W, 6 W, 3 M) 91-108 minutes

Domain	Subdomain	Instrument	Administration Time	Order of Administration In person (~98 min)
		Assessment of Speech Intelligibility*	2 min	1, and as needed
Screening	Screening	Galveston Orientation and Amnesia Test (GOAT)*	5 min	2, and as needed
History	Participant Interview	Interview to update occupational status; living situation; medical history (e.g., known neurologic, cognitive, psychiatric conditions)*	10 min#	3
Daily/Global Function	Global Outcomes	Glasgow Outcome Scale Extended (GOSE)*	15 min	5
		Functional Status Exam (FSE)*	10 min	4
Psychological Health/ Neurobehavioral Symptoms	Depression, Anxiety, Somatic	Brief Symptom Inventory-18 (BSI-18)*	3 min	13
	TBI-Related Symptoms	Rivermead Post Concussion Symptoms Questionnaire (RPQ)*	3 min	11
	Post-traumatic stress	PTSD Checklist for DSM-5 (PCL-5)*	3 min	12
	Suicide	Columbia Suicide Severity Rating Scale Screening Version + (C-SSRS)*	5 min	As needed
	Life Quality (Brain)	Quality of Life after Brain Injury Overall Scale (QoLIBRI-OS)*	3 min	7
Symptom Validity	Symptom Validity	Structured Inventory of Malingered Symptomatology (SIMS)*	10 min	6
Cognitive Performance	Episodic Memory	Rey Auditory Verbal Learning Test (RAVLT)	15 min	8 (delay after BSI- 18)
	Executive Function	Trail Making Test A+B	5 min	9
	Processing Speed	Wechsler Adult Intelligence Scale – 4th Edition Processing Speed Index (WAIS-IV) PSI	4 min	10
Matar	Fine motor (Bradykinesia)	Finger tapping	5 min	14
Motor	Gross motor/mobility	Short Physical Performance Battery (SPPB)	5 min	15

<sup>+Triggered by /BSI-18

\*The SAC can only be collected in-person, and cannot be collected by telephone.

\*Measures that should be collected over the phone

## 8.3 Abbreviated Assessment Battery (AAB) (2 W, 6 W, 3 M) 60-67 minutes

Domain	Subdomain	Instrument	Administration Time	Order of Administration In person (~72 min)
Screening	Screening	Assessment of Speech Intelligibility*	2 min	1, and as needed
		Galveston Orientation and Amnesia Test*	5 min	2, and as needed
Consciousness and Basic Cognition	Confusion	Confusion Assessment Protocol (CAP)	15 min	Determined by Flexible Outcome Battery Flow Chart (page 18 of TRACK-TBI
	Consciousness	Coma Recovery Scale Revised (CRS-R)	15-30 min	Outcomes SOP V 10)
Daily/Global Function	Global Outcomes	Glasgow Outcome Scale Extended (GOSE)*	15 min#	3
		Disability Rating Scale (DRS)*	10 min#	4

\*Measures that should be collected over the phone

#### 9 TRACK-TBI PRECISION MEDICINE ASSESSMENT BATTERY: DESCRIPTION OF MEASURES

## 9.1 Measures to Screen Competency and Selection of Battery

## Speech Intelligibility

This measure is administered and scored in the same way as described in the TRACK-TBI Outcomes Assessment SOP. The Speech Intelligibility measure is administered at the beginning of the assessment to determine if the Abbreviated Assessment Battery should be administered and whether to administer the CAP and/or CRS-R. This measure can also be administered at any point during a phone or in-person assessment, if the study coordinator has any concerns about the participant's capacity to consent and complete an assessment.

